5. PROTOCOL SYNOPSIS

5.1. Synopsis

Title:	A Multi-Center, Open-Label, Long-Term Safety Study of S5G4T-1 to Evaluate the Safety of S5G4T-1 in Papulopustular Rosacea Patients
Study Number:	SGT-54-07
Study Phase:	3
Indication:	Papulopustular rosacea
Study Period:	In treatment period: up to 52 weeks (365 days)
Study Products:	S5G4T-1: Encapsulated Benzoyl Peroxide (E-BPO) Cream, 5%, developed by Sol-Gel Technologies and manufactured by [REDACTED], Montreal, Canada.
Study Objectives:	To assess the safety of S5G4T-1 when applied once daily for up to 52 weeks in patients with papulopustular rosacea.
Study Design:	
Patients from the double-blind, Phase 3 studies SGT-54-01 and SGT-54-02 may continue into this open-label, long-term safety study. Patients will be admitted into the study only after a written informed consent has been obtained and after completing Visit 6 within the Week 12 window and not missing more than 1 visit of Visits 3, 4 or 5 in these studies. Eligible patients for enrollment may apply the study product, S5G4T-1, daily for up to 40 weeks to complete long-term usage of the drug for up to 52 weeks.
 
The sponsor may also recruit patients for the long-term safety study only (and not as an extension study for phase 3) for a total of 52 weeks. In this case, the subject must meet the same inclusion and exclusion criteria as the phase 3 SGT-54-01 or SGT-54-02 studies, see section 12.2 and 12.3. The study will enroll patients who completed the SGT-54-01 and SGT-54-02 studies first. Study sites should not enroll new patients into SGT-54-07 until the Sponsor provides approval to do so.
 
The Sponsor may terminate the recruitment after 300 patients complete a total of 28 weeks and 100 patients complete a total of 52 weeks of treatment.

Study Population:	Approximately 700 male and female patients who meet the study Entry Criteria (applies for patients who completed Study SGT-54-01 or SGT-54-02) or who meet the Inclusion/Exclusion criteria (applies for new patients) will be enrolled with the intent that at least 300 patients will be followed for 28 weeks and at least 100 patients will be followed for 52 weeks. Drop-out patients will not be replaced.
Investigational Sites	It is estimated that up to 56 study centers in US will participate in this study.

Dosing:	Patients will apply the study product if applicable once daily for up to 52 weeks. Patients will use a “pea-size” amount for each area of the face (chin, left cheek, right cheek, nose, left forehead and right forehead). The Study product will be spread as a thin layer in such a way as to provide an even distribution, avoiding the eyes, lips, inside the nose, mouth and all mucous membranes. Patients will receive detailed instructions on the method of application and quantity to use in order to assure that treatment is harmonized among all patients to best extent possible.
----------------	---


Methodology:
	
Clinical and Safety Evaluations will be performed at:
 
 1. Visit 1/Screening, only applies for new patients 2. Visit 2/Baseline, Day 1 can also be Visit 6/Week 12, Day 85 of Study SGT-54-01 or Study SGT-54-02 3. Visit 3/Week 4, Day 29 (\pm 10 Days) 4. Visit 4/Week 8, Day 57 (\pm 10 Days) 5. Visit 5/Week 12, Day 85 (\pm 10 Days) 6. Visit 6/Week 16, Day 113 (\pm 10 Days) 7. Visit 7/Week 20, Day 141 (\pm 10 Days) 8. Visit 8/Week 24, Day 169 (\pm 10 Days) 9. Visit 9/Week 28, Day 197 (\pm 10 Days) 10. Visit 10/Week 32, Day 225 (\pm 10 Days) 11. Visit 11/Week 36, Day 253 (\pm 10 Days) 12. Visit 12/Week 40, Day 281 (\pm 10 Days)/ End of Treatment/End of Study for patients who complete the study, early terminate, or if the Sponsor terminates the study prematurely (only for patients that completed Study SGT-54-01 or Study SGT-54-02) 
Applies for new patients:
 
 13. Visit 13/Week 44, Day 309 (\pm 10 Days) 14. Visit 14/Week 48, Day 337 (\pm 10 Days) 15. Visit 15/Week 52, Day 365 (+ 10 Days)/ End of Treatment/End of Study for patients who complete the study, early terminate, or if the Sponsor terminates the study prematurely. 
Patients will be admitted into the study only if they completed Study SGT-54-01 or Study SGT-54-02 at Week 12 within the window time or missed no more than one study Visit 3, 4 or 5 in these studies. For patients that were enrolled for study SGT-54-01 or study SGT-54-02 clinical exclusion criteria (IGA grade or lesion count) will not limit the enrollment for the study. New patients who meet specified inclusion criteria (including moderate to severe rosacea according to 5-point IGA scale and have a minimum total of 15 and a maximum total of 70 inflammatory lesions (papules and/or pustules) including those present on the nose) and none of the exclusion criteria will be admitted to the study.
 
At each visit a 5-point IGA scale of rosacea; rosacea erythema, and telangiectasia; will be performed and recorded. If a patient is assessed as “mild”, “moderate” or “severe” (2, 3 or 4 respectively), study product will be dispensed and the patient will use the study product daily according to patient instructions. If a patient is assessed as “clear” (0) or “almost clear” (1), the patient will not be dispensed the study product.
 
In addition, at each visit, the following safety measures will be recorded: monitoring for any AE including local and systemic; investigator Cutaneous Safety Assessment rating of erythema, dryness and scaling and

----------------------------	---

	
Local Tolerability Assessments rating of itching and burning/stinging on a scale ranging from 0 (None) to 3 (Severe).
 
Rosacea Quality of Life Questionnaire (RosaQoL) will be completed at Baseline, Visits 5, 8, 11, 14 and at End of Study or at early termination. The RosaQoL data of patients who were enrolled from SGT-54-01 or SGT-54-02, will be used from the questionnaire completed at Visit 6/Week 12 of SGT-54-01 or SGT-54-02. Urine pregnancy tests will be performed on females of child-bearing potential at Screening (for new patient) and Baseline, and every 4 weeks during study or at early termination.
 
Regardless of the duration of the study, patients that exhibit serious adverse event (SAE), will be followed up until the SAE stabilizes or resolves, based on investigator's medical judgment.

--	---

Clinical Trial Duration	
Up to 52 weeks/365 days.
 
The Sponsor may terminate the study once 100 patients complete a total of 52 weeks and 300 patients complete a total of 28 weeks of treatment (totals include 12 weeks from the double-blind treatment period of Study SGT-54-01 or Study SGT-54-02 for those previously enrolled in this studies).
 
Patients have the right to stop the study for any reason at any given time.

Study product dosage and Reference therapy	
Encapsulated Benzoyl Peroxide Cream, 5% will be dispensed every 4 weeks.
 
The study product will be supplied in 55-gram pumps (total weight including pump is 85 grams).

Entry Criteria (applies for patients entering from Phase 3, SGT-54-01 or SGT-54-02)	
Patients rolling over from either Study SGT-54-01 or Study SGT-54-02 may participate in the study if they meet the criteria below:
 
 1. Patient must sign an Institutional Review Board (IRB) approved written informed consent for the extension study. 2. Complete 12 weeks or within the Week 12 window time (\pm 4 days) of the double-blind treatment period of Study SGT-54-01 or Study SGT-54-02 and missed not more than one visit of Visits 3, 4 or 5 in Study SGT-54-01 or Study SGT-54-02. 3. Patients who in the opinion of the investigator, are likely to be able to follow the restrictions of the protocol and complete the study.
Patient Inclusion Criteria (applies for new patients only)	
New patients who were not previously enrolled in Study SGT-54-01 or Study SGT-54-02 must meet all the following criteria:
 
 1. Patient must sign an Institutional Review Board (IRB) approved written informed consent for this study. 2. Male and female 18 years of age and older. 3. Patients must have clinical diagnosis of moderate to severe rosacea with a Baseline Investigator's Global Assessment (IGA) Score of 3 (moderate severity) or 4 (severe) on a severity scale of 0 to 4. 4. Have a minimum total of 15 and a maximum total of 70 inflammatory lesions (papules and/or pustules) including those present on the nose. 5. Have two nodules or less (nodule defined as a papule or pustule greater than 5 mm in diameter) at Baseline. 6. Patients must be willing and able to understand and comply with the requirements of the study, apply the medication as instructed, refrain from use of the following medications (during the study, return for the required treatment period visits, comply with therapy prohibitions, and are able to complete the study): 
 – topical rosacea medication including: Metronidazole 0.75% to 1%, Azelaic acid, Brimonidine, Oxymetazoline, Sodium Sulfacetamide 10%, Sulfur 5%, Benzoyl Peroxide, Clindamycin,

	
Erythromycin, Benzoyl Peroxide and Clindamycin, Sulfur lotions, retinoids, Ivermectin Cream 1%, Ivermectin lotion 0.5%; or
 
– topical and systemic (oral and injectable) antibiotics known to impact rosacea e.g., tetracycline and its derivatives, erythromycin and its derivatives, doxycycline and its derivatives, minocycline and its derivatives, azithromycin and its derivatives, clarithromycin and its derivatives, metronidazole and its derivatives, sulfamethoxazole, or trimethoprim and retinoids (e.g., isotretinoin).
 
7. Patients must be willing to minimize or not significantly alter controllable external factors that might trigger rosacea flare-ups (such as spicy food, thermally hot foods, soups and drinks, hot environments, prolonged sun exposure, strong winds, alcoholic beverages, etc.) throughout their participation in the study.
 
8. Patients must be generally healthy and free from any clinically significant disease, other than rosacea, that might interfere with the study evaluations.
 
9. Sexually active females of child-bearing potential, excluding women who are sterilized (including Essure procedure, tubal ligation, bilateral oophorectomy or hysterectomy) or post- menopausal for at least 2 years, must use one of the following birth control options*:
 
 • Intrauterine device (IUD) • Hormonal (injections, implants, transdermal patch, vaginal ring) • Abstinence • Oral contraceptives • Female condom • Diaphragm with spermicides • Cervical cap with spermicides • Contraceptive sponge 
* In addition, patients entering the trial that are on hormonal contraceptives must have been on this method for at least 3 months (90 days) prior to the trial and continue the method for the duration of the trial. Patients who had used hormonal contraception and stopped must have stopped no less than 3 months prior to Baseline. Patients entering the study who had an Essure procedure must have had this procedure at least 3 months prior to the study and have undergone an Essure confirmation test to ensure its efficacy. A sterile sexual partner is not considered an adequate form of birth control.

Patient Exclusion Criteria (applies for new patients only):
	
Patients who were not previously enrolled in Study SGT-54-01 or Study SGT-54-02 must be excluded from entry into the study according to the following criteria:

	
1. Females, who are pregnant, breastfeeding, or planning a pregnancy within the period of their study participation or were found to have positive pregnancy test at baseline or screening visits.2. Presence of more than 2 facial nodules or any nodule greater than 1 cm.3. Current or past ocular rosacea (e.g., conjunctivitis, blepharitis, or keratitis) of sufficient severity to require topical or systemic antibiotics.4. Presence of any other facial skin condition that might interfere with rosacea diagnosis and/or assessment including but not limited to (e.g., on the face: rosacea conglobata, rosacea fulminans, acne vulgaris, acne conglobata, acne fulminans, or secondary acne (chloracne, drug-induced acne, etc.), facial pustulosis of the chin, dermatitis (including peri-orbital and seborrheic dermatitis), demodicidosis, facial keratosis pilaris, acute lupus erythematosus, psoriasis, eczema, acneiform eruptions caused by medications, steroid acne, steroid folliculitis, sunburn, rhinophyma, or bacterial folliculitis).5. Any uncontrolled, chronic or serious disease or medical condition that would prevent participation in a clinical trial or, in judgment of the Investigator, would put the patient at undue risk or might confound the study assessments.6. Excessive facial hair (e.g., beards, sideburns, moustaches, etc.) that would interfere with diagnosis or assessment of rosacea.7. History of unresponsiveness to topical benzoyl peroxide.8. Concurrent use of drugs causing acneiform eruptions (e.g., azathioprine, haloperidol, halogens, lithium, systemic corticosteroids, phenytoin, phenobarbital, testosterone, anabolic steroids, isoniazid).9. Known sensitivities to the study product ingredients. Allergy to benzoyl peroxide, parabens and glycerin or other ingredients listed in the investigator brochure.10. Use:
– within 180 days prior to Baseline or during the study of oral retinoids (e.g., Accutane[®]) or therapeutic vitamin A supplements of greater than 10,000 units/day (multivitamins are allowed).– within 90 days prior to Baseline or during the study radiation therapy and/or anti-neoplastic agents.– start or change of dose within 90 days prior to Baseline or during the study of vasodilators, vasoconstrictors, anticoagulation or beta-blockers therapy and use throughout the study. Use of such therapy must remain constant throughout the study.– start or change of dose within 90 days prior to Baseline of hormonal treatment (oral, implanted, topical contraceptives and
--	--

	
androgens). Use of such therapy must remain constant during the study.
 
 – within 30 days prior to Baseline or during the study of therapeutic Vitamin D supplements of greater than 2,000 units/day (daily multivitamins with Vitamin D not exceeding more than 2000 IU/day are allowed). If a patient on a constant stable prescribed weekly dose, they should remain on this dose during the study. – within 30 days prior to Baseline or during the study of (1) systemic steroids, (2) topical retinoids to the face (e.g., tretinoin) (3) systemic (e.g., oral or injectable) antibiotics known to impact rosacea (e.g., tetracycline and its derivatives, erythromycin and its derivatives, doxycycline and its derivatives, minocycline and its derivatives, macrolides and its derivatives, azithromycin and its derivatives, clarithromycin and its derivatives, metronidazole and its derivatives, sulfamethoxazole, bactrim or trimethoprim); short term treatment of all other antibiotics (not affecting rosacea for) ≤ 14 days for non-rosacea related conditions is acceptable, (4) immunosuppressive agents, or immunomodulators (e.g. cyclosporine, tacrolimus, pimecrolimus). – of medicated make-up (including anti-aging make-up) throughout the study and significant change in the use of consumer products within 14 days of study entry and throughout the study. – of niacin and niacinamide (Vitamin B3) within 24 hours of study entry and throughout the study. – of intranasal and inhaled corticosteroids do not require a washout and may be used throughout the study if at a stable and standard dose. 
11. Facial use within 14 days prior to Baseline or during the study of (1) topical steroids, (2) topical anti-inflammatory agents or topical non-steroidal anti-inflammatory drugs (NSAID), (3) topical antimycotics, (4) any topical rosacea treatments (e.g., Metronizadole 0.75% to 1%, Azelaic acid, Brimonidine, Oxymetazoline, Sodium Sulfacetamide 10%, Sulfur 5%, Benzoyl Peroxide, Clindamycin, Erythromycin, Benzoyl Peroxide and Clindamycin, Sulfur lotions, Retinoids, Ivermectin) or (5) topical antibiotics.
 
12. Use on the face within 30 days prior to Baseline or during the study of (1) cryodestruction or chemodestruction, (2) dermabrasion, (3) photodynamic therapy, (4) acne surgery, (5) intralesional steroids, (6) laser resurfacing or electrodesiccation, (7) x-ray therapy, (8) pulse dye laser, (9) long-pulsed Nd-YAG laser, (10) Intense pulse light or pulse light laser, (11) electrocautery or electrocoagulation, (12) CO₂ laser, Fractioned lasers, or loop electrosurgery, (13) facial peels or other facial cosmetic surgery (e.g., Thermage[®], etc.).

--	--

	
 13. Use of medicated cleansers on the face (e.g., benzoyl peroxide, salicylic acid, sulfur or triclosan) within 7 days of Baseline and throughout the study. 14. Patient consumes excessive alcohol, abuses drugs, or has a condition that could compromise the patient's ability to comply with study requirements and/or have drug or alcohol addiction requiring treatment in the past 12 months. 15. Use of topical astringents or abrasives (e.g., rubs, exfoliating cleansers and products containing salicylic acid and/or alcohol), topical preparations that contain spices or lime, medicated topical preparations (prescription and OTC products) within 7 days prior to Visit 2 (Baseline) and throughout the study. 16. Use of antipruritics (including antihistamines), spa or sauna treatments or chlorine exposure (swimming pool etc.) within 24 hours (1 day) of all study visits (Visit 2, Baseline, through End of Study). 17. Participation in any clinical study involving an investigational product, agent or device that might influence the intended effects or mask the side effects of study product, within 30 days prior to Visit 2 (Baseline) and throughout the study. 18. Previous enrollment in this study or current enrollment in this study at another participating site. 19. Employee (or employee's family member) of the research center or private practice, or patients who have a conflict of interest. 20. Patients living (e.g., siblings, spouses, relatives) in the same household cannot be enrolled in the study at the same time. 21. Use of tanning booths, sun lamps or excessive UV radiation (e.g., phototherapy, daily extended exposure or occupational exposure to the sun), sunbathing or excessive exposure to the sun 1 week (7 days) prior to Baseline and throughout the study. 22. Patients who in the opinion of the investigator, are unlikely to be able to follow the restrictions of the protocol and complete the study.
Safety Endpoints:	
 • Adverse events (AEs), including serious adverse events (SAEs) occurring at any time during the trial. • Investigator Cutaneous Safety Assessment and Local Tolerability Assessments score at any time during the trial.
Safety:	
The incidence of all adverse events reported during the study will be summarized. Safety will be evaluated by comparing the nature, severity and frequency of their adverse event profiles. Safety variables include Investigator Cutaneous Safety Assessment score, treatment-emergent adverse events (AEs), SAEs, treatment related AEs, AEs leading to study discontinuation and concomitant medications

Statistical Method:	
General Statistical Methodology
 
All statistical processing will be performed using SAS® version 9.3 or later unless otherwise stated. Data will be summarized using descriptive statistics. No inferential testing or imputations for missing data will be performed. No interim analyses are planned for the co-primary variables. For categorical parameters, the number and percentage of patients in each category will be presented. For continuous parameters, descriptive statistics will include n (number of patients), mean, standard deviation, median, minimum and maximum.
 
Populations Analyzed
 
All analyses will be performed using the Safety Population of the study. Part of this population will be referred as the extension safety population, and part as a new enrolled safety population. All patients who receive at least one confirmed dose of S5G4T-1 (in either Study SGT-54-01 or Study SGT-54-02, and in this study or for new patients in this study) and have at least one assessment will be included in the Safety Population.
 
The number of patients included in the Safety Population will be summarized.
 
Analysis of Efficacy
 
This study is not intended to assess efficacy, but rather the IGA is included to determine the need for treatment and subsequent re-treatment. after the initial 12-week treatment course (in either Study SGT-54-01 or Study SGT-54-02 or for those patients not previously enrolled in Study SGT-54-01 or Study SGT-54-02) and any subsequent 4-week courses, if applicable. Certain efficacy data and endpoints will, however, be summarized.
 
Descriptive statistics will be used to summarize the assessment of efficacy. IGA scores will be summarized at Baseline Visit of Study SGT-54-01 or Study SGT-54-02 or at the Screening visit of SGT-54-07 for those patients not previously enrolled in Study SGT-54-01 or Study SGT-54-02, and entry into the study (SGT-54-07) and every 4 weeks through end of the study. The number and percentage of patients who achieve treatment success at the scheduled study visits will be tabulated. A patient will be considered a success if their IGA score is clear or almost clear.
 
Rosacea Quality of Life Questionnaire (RosaQoL) will be completed at Baseline, Visits 5, 8, 11, 14 and End of Study visits. The RosaQoL data of patients who were enrolled from SGT-54-01 or SGT-54-02, will be used from the questionnaire completed at Visit 6/Week 12 of SGT-54-01 or SGT-54-02.

----------------------------	---

Safety Evaluation:	Safety will be evaluated by tabulations of adverse events (AEs), Cutaneous Safety Assessments (dryness and scaling), Local Tolerability Assessment (itching and burning) and assessments for erythema and telangiectasia will be presented with descriptive statistics at Baseline and at the scheduled study visits. Frequencies and percentages for each outcome category will be included in these statistics. Safety data will be presented for patients in the Safety Population with tabulations for the following periods 12 to 28 weeks, > 28 to 52 weeks and > 52 weeks to the end of the study, as well as an overall for all periods.
---------------------------	--

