8. OBJECTIVE

The objective of this long-term safety study is to determine the nature, severity and frequency of the AE rate, the Cutaneous Safety Assessment and the Local Tolerability Assessment of S5G4T-1 when applied once daily, if applicable, for up to 52 weeks

The safety endpoints to be assessed include the following:

- The frequency of both local and systemic adverse events
- Investigator Cutaneous Safety Assessment (dryness and scaling) and Local Tolerability Assessment (itching and burning/stinging) at Baseline and at all study visits.

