11. OVERALL STUDY DESIGN

Approximately 700 patients will be enrolled at up to 56 sites. All patients in this open-label, long-term safety study will be assigned to treatment with S5G4T-1.

Patients who complete the treatment period of the Phase 3 studies SGT-54-01 or SGT-54-02 will be offered to continue into this long-term safety, open-label extension study for up to an additional 40 weeks. These patients will be admitted into the study and assigned to S5G4T-1 only after completing Visit 6/Week 12 within the allowable window (\pm 4 days) and without protocol violation of missing visits (i.e., missing more than one of Visits 3, 4 or 5).

New patients with moderate to severe rosacea (rated 3 or 4 on the 5-point IGA scale) will be enrolled into this long-term safety, open-label study for 52 weeks. These patients will be admitted to this study after meeting inclusion/exclusion criteria. Subjects with severe rosacea who are appropriate for systemic treatment need to be counseled regarding their treatment options by the Principal Investigator. [The study will enroll patients who completed the SGT-54-01 and SGT-54-02 studies first. Study sites should not enroll new patients into SGT-54-07 until the Sponsor provides approval to do so.](#)

The objective of this study is to determine the long-term safety and tolerability of daily use of S5G4T-1 in papulopustular rosacea patients.

Patients who successfully completed the 12-week treatment period from Study SGT-54-01 or Study SGT-54-02 may be offered to continue in the long-term safety, open-label extension study (Study SGT-54-07) for up to an additional 40 weeks [sum of up to 52 weeks; 12 weeks treatment during the double-blind, pivotal studies (Study SGT-54-01 or Study SGT-54-02) and up to an additional 40 weeks in this long-term safety study (Study SGT-54-07)]. The Sponsor may terminate the study once 300 patients complete a total of 28 weeks of treatment and 100 patients complete a total of 52 weeks.

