13.2. Screen Failure and Discontinuation Criteria

For new patients, a screen failure is a patient who is not randomized/enrolled in the study due to ineligibility, after signing an Informed Consent Form, and did not receive study product. The Informed Consent Form signed by the patient should be kept with the source document for patients who do not pass the screening procedures. The documentation should include identification of the eligibility criterion or criteria that were and were not met. The patient should not be re-screened for this study without Sol-Gel's approval.

Although encouraged to complete the study whenever possible, patients are free to discontinue their participation in this study at any time and for any reason without prejudice. A patient may be withdrawn from the study prior to study completion for any of the following reasons:

- Investigator opinion that it is not in the patient's best interest to continue.
- Patient Request /Withdraw Consent – Whenever the patient decides it is in his/her best interest to withdraw.
- Adverse Event – when the investigator thinks it's in the patient's best interest
- Lost to Follow-up – Documentation confirmed at minimum by two phone calls and certified letter. Best effort should be performed to capture an explanation for the lost-to follow-up event.
- Protocol Violation – When requirements of the protocol are not respected, especially when patient safety is concerned.
- Pregnancy
- Worsening of condition that requires alternate therapy.

In the event that the Sponsor terminates the study early, every effort will be made to allow patients to complete at least 6 months of treatment.

In the case of patients who discontinue due to an Adverse Event, the Investigator will conduct follow-up contacts with the patient until the Investigator, Sponsor and Medical Monitor agree the event is satisfactorily resolved and/or stabilized.

Patients discontinued early from the study shall not be replaced.

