14. CLINICAL OUTCOME ASSESSMENTS

14.1. Investigator Global Assessment (IGA)

The IGA will be performed at all study visits.

If a patient is assessed as “clear” (0) or “almost clear” (1), the patient will not be dispensed the study product. If a patient is assessed as “mild”, “moderate” or “severe” (2, 3 or 4, respectively), study product will be dispensed and the patient will use the study product daily according to patient instructions.

In the event a subject is not dispensed IP at a given visit due to an IGA of "clear" or "almost clear," and the subject's rosacea condition worsens, an unscheduled visit can be performed for assessing the subject and dispensing IP, if appropriate.

The IGA scale provided in [Table 1](#) will be used to describe the severity grade and subsequent score:

Table 1: Investigator Global Assessment (IGA) Scale

Grade	Description
0 – Clear	Skin clear of inflammatory papules or pustules
1 – Almost Clear	Very few small papules or pustules and very mild dull erythema is present
2 – Mild	Few small papules or pustules and mild dull or light pink erythema is present
3 – Moderate	Several to many small or larger papules or pustules and moderate light to bright red erythema is present
4 – Severe	Numerous small and/or larger papules or pustules and severe erythema that is bright red to deep red is present

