18.3. Analysis of Efficacy

This study is not intended to assess efficacy, but rather the IGA is included to determine the need for treatment and subsequent re-treatment after treatment course (in either Study SGT-54-01 or Study SGT-54-02 or for new patients not previously enrolled in Study SGT-54-01 or Study SGT-54-02) and any subsequent 4-week courses, if applicable. Certain efficacy data and endpoints will, however, be summarized.

Descriptive statistics will be used to summarize the assessment of efficacy. IGA scores will be summarized at Baseline Visit of Study SGT-54-01 or Study SGT-54-02 or at the Screening visit of SGT-54-07 for those patients not previously enrolled in Study SGT-54-01 or Study SGT-54-02, and entry into the study (SGT-54-07) and every 4 weeks through end of the study. The number and percentage of patients who achieve treatment success at the scheduled study visits will be tabulated.

The number of retreatments is defined as the number of clinical confirmations of the condition for which the subject was initially treated after the first treatment period with S5G4T-1. For rollover subjects previously treated with Vehicle Cream, this is the number after the initial treatment in Study SGT-54-07. For rollover subjects previously treated with S5G4T-1, this is the number of treatments in Study SGT-54-07 following the cessation of the treatment which began in Study SGT-54-01 or Study SGT-54-02.

The number of treatment free days until the first retreatment (relapse) will be calculated and analyzed. For rollover subjects previously treated with Vehicle Cream, the number of treatment free days will be the number of days between the end of the initial treatment in study SGT-54-07 and the start of the next treatment in study SGT-54-07 if one should be needed or the end of the subject's participation in study SGT-54-07. For rollover subjects previously treated with S5G4T1, the number of treatment free days will be the of days between the end of the initial treatment that began in Study SGT-54-01 or Study SGT-54-02 and the start of the next treatment in study SGT-54-07 if one should be needed or the end of the subject's participation in the study SGT-54-07.

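### The optional stop rule credits 12 double-blind weeks to vehicle patients too, so it can be met with fewer than 100 patients at 52 weeks from first S5G4T-1 dose

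*Protocol*

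**What the plan says.** Protocol 5.1 (Clinical Trial Duration) lets the sponsor end the study when 100 patients have a total of 52 weeks and 300 a total of 28 weeks of treatment. It adds in brackets that "totals include 12 weeks from the double-blind treatment period of Study SGT-54-01 or Study SGT-54-02 for those previously enrolled in this studies". Prior enrolment is the only condition for the credit.

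The same counts appear in three other places:

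- Protocol 5.1 (Study Design): "The Sponsor may terminate the recruitment after 300 patients complete a total of 28 weeks and 100 patients complete a total of 52 weeks".
- Protocol 11 gives the sponsor the option to "terminate the study once 300 patients complete a total of 28 weeks of treatment and 100 patients complete a total of 52 weeks". The sentence before it builds the rollover total from "12 weeks treatment during the double-blind, pivotal studies" plus up to 40 weeks in this study.
- SAP 6.1: the same rule, again with 52 weeks as the most a rollover can accumulate.

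None of these says whose 12 weeks count.

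Vehicle patients do roll over. Protocol 18.3 defines the retreatment count for them: "For rollover subjects previously treated with Vehicle Cream, this is the number after the initial treatment in Study SGT-54-07". The SAP starts their clock in SGT-54-07. Section 8.9.2 classes their parent-study adverse events as arising before treatment, and the analysis-visit table in 8.1.3 has no data source for them at Weeks 44, 48 and 52.

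**The concern.** The objective (Protocol 8) is the safety and tolerability of "S5G4T-1 when applied once daily, if applicable, for up to 52 weeks". The counts of 100 and 300 are the only adequacy targets in either document; SAP 9 offers no derivation beyond a minimum requirement for a long-term safety study. The stop rule and the analysis run on different clocks. A vehicle rollover who finishes Week 40 is a 52-week patient for stopping and a 40-week patient in every summary.

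If the sponsor used the option as soon as it opened, the study could close with fewer than 100 patients observed to 52 weeks from first S5G4T-1 dose. Information on events that first arise after Week 40 would then be thinner than the target implies. SAP 10 reports that no new patients were enrolled, so only S5G4T-1 rollovers can reach 52 weeks. The timing of adverse events is not affected, because SAP 8.9.2 already runs its periods from first S5G4T-1 application. The issue is when the study may stop.

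**Working it through.** **Inputs from the documents.** Thresholds of 100 and 300, and a 12-week credit (Protocol 5.1). Rollovers end at Week 40, Day 281 ± 10 (Protocol 5.1, 5.2). The Week 16 visit is Day 113. The SAP targets are Day 197 for Week 28 and Day 365 for Week 52 (SAP 8.1.3). Planned enrolment is about 700.

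**Input not in the documents.** The arm mix of credited patients. Let s be the S5G4T-1 share. I show 1:1, 2:1 and 3:1 (S5G4T-1 to vehicle), and a case with only 10% vehicle.

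**1. Reproduce the plan's figure.** 12 + 40 = 52 weeks; in days, 84 + 281 = 365. For 28 weeks, 12 + 16 = 28.

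**2. Apply it to a vehicle rollover.** Weeks from first S5G4T-1 dose: 0 + 40 = 40, taking first dose at SGT-54-07 Baseline. It is less if product was withheld at Baseline. Shortfall against Day 365: 365 − 281 = 84 days, or 365 − 291 = 74 at the latest in-window visit. On the 28-week count the credit arrives at Day 113, which is 197 − 113 = 84 days early.

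**3. True counts if the study stops at the 100th credited completer, with equal retention by arm.**

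- 52 weeks: 100 × s.
- 28 weeks, lower limit: 100 + 200 × s. The 100 who reached Week 40 all have at least 28 weeks from first dose. Of the other 200 credited patients, only the S5G4T-1 share is certain to.

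**4. Credited patients needed for the true targets.**

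- 52 weeks: c = 100 / s, rounded up.
- 28 weeks: c + (300 − c) / s, rounded up.

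**5. Illustration.** The 95% upper bound for an event first arising after Week 40 and never seen is 1 − 0.05^(1/n), with n the true 52-week count. It is 2.95% at n = 100.

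| Vehicle share | True 52-week count | 28-week lower limit (of 300) | Credited at 52 weeks for 100 true (% of 700) | Credited at 28 weeks for 300 true | Zero-event bound |
|---|---|---|---|---|---|
| 10% | 90 | 280 | 112 (16%) | 321 | 3.3% |
| 25% (3:1) | 75 | 250 | 134 (19%) | 356 | 3.9% |
| 1/3 (2:1) | 67 | 233 | 150 (21%) | 375 | 4.4% |
| 50% (1:1) | 50 | 200 | 200 (29%) | 400 | 5.8% |

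**6. Sensitivity to retention.** At 2:1, s = 2 / (2 + r), where r is vehicle retention divided by S5G4T-1 retention. With r = 0.8, 2 / 2.8 gives 71 true 52-week patients; with r = 1.25, 2 / 3.25 gives 62.

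**7. Could all 100 be S5G4T-1 patients by chance?** Even at a 10% vehicle share the probability is 0.9^100 = 2.7 × 10⁻⁵.

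**The case against.** The strongest reply is that the rule counts weeks of treatment in a study of S5G4T-1, so treatment should be read as S5G4T-1 treatment. Protocol 5.1 (Study Design) also speaks of 52 weeks of use of the drug. That reading does not survive the bracketed credit, which is explicit and conditions only on prior enrolment, or Protocol 11, which calls the whole double-blind period treatment. The remark about drug use assumes that all 12 earlier weeks were on drug, which is untrue for vehicle patients.

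SAP 2 says the SAP prevails over the protocol, and SAP 6.1 omits the bracket. But SAP 6.1 keeps the total of up to 52 weeks and is equally silent on arm, so it does not remove the credit.

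The Study Population text in Protocol 5.1 separately states an intent to follow at least 100 patients for 52 weeks, without mentioning the credit. If that means follow-up on S5G4T-1, the stop rule can defeat it.

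Another objection is that weeks from first application are calendar weeks, and at IGA 0 or 1 "the patient will not be dispensed the study product". That is true, but 12 + 40 is already calendar time, so counting from first application does not loosen the rule. Weeks of actual use are a separate question.

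Some of the case stands. Stopping is optional. The arm ratios and the stop at exactly the 100th completer are assumptions. The zero-event bound belongs to no planned analysis. Exposure by prior arm is tabulated, so a shortfall would show in the report, though only afterwards. Enrolment is complete (SAP 10), so the recruitment sentence no longer matters in practice. Protocol 13.2 says "every effort will be made to allow patients to complete at least 6 months of treatment" on early termination, which softens the 28-week count but does nothing for the 52-week count.

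**Conclusion.** The concern holds. As written, the stop option can open with fewer than 100 patients at 52 weeks from first S5G4T-1 dose. One vehicle rollover among the first 100 credited completers is enough, whatever the allocation ratio.

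The size of any shortfall is uncertain. If the study stops at the 100th credited completer with equal retention, the true count is about 50 to 75 over ratios of 1:1 to 3:1. There is no expected 52-week shortfall once about 134 to 200 credited completers exist. That is well below 700, but the documents give no dropout rate. The missing arm condition is certain; an actual shortfall is not. It should be fixed because it is a decision threshold that contradicts the SAP's own clock.

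**What to change.** In Protocol 5.1 (Clinical Trial Duration), Protocol 11 and SAP 6.1, state that the 28- and 52-week totals are counted from first application of S5G4T-1, and that the 12 double-blind weeks are added only for patients who received S5G4T-1 in SGT-54-01 or SGT-54-02. Change the recruitment sentence in Protocol 5.1 (Study Design) in the same amendment for consistency. If the parent studies are still blinded, the count should come from someone with access to the allocation, such as an unblinded statistician.

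Optionally, add to SAP Table 14.3.0.1 the numbers of patients with at least 28 and at least 52 weeks since first S5G4T-1 dose. Table 14.2.1.2 already plans counts by visit from first dose. However, its shells for Weeks 44 to 52 put data under the vehicle column and NA under the E-BPO column, the reverse of SAP 8.1.3, and should be corrected.

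**Cost.** A protocol amendment with IRB approval before use (Protocol 19.2) at up to 56 sites, a matching SAP edit, and an arm-specific count. The option may open later: at 2:1, about 150 credited Week 40 completers instead of 100 and about 375 credited 28-week patients instead of 300. Over 3:1 to 1:1 the ranges are 134 to 200 and 356 to 400. These are expected values; for a 90% chance of at least 100 true 52-week patients the completer counts are 142, 161 and 218 at 3:1, 2:1 and 1:1. All are below the planned 700, but feasibility depends on dropout, which is not stated.
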